4.10.2 Qualitative analysis

Self-reported patient experience will be examined at 6 and 12 months using qualitative methods. Interview transcripts will be imported into NVivo for thematic analysis. Initial open coding of transcripts will be undertaken iteratively by members of the research team. Themes and care quality measures will be presented to the broader research team and program implementers for final consensus.

4.10.3 Economic analysis

The analysis will be conducted from a health service perspective (base case) and a societal perspective including direct and indirect costs from the health-consumer's perspective - out of pocket expenses for any medicines or products provided, waiting time and travel time to attend treatment, productivity gains or time lost from work.

The scope of the within-study cost analysis is constrained by the design of the cohort study. Cost items associated with the co-design process, research and evaluation will be excluded. Resource use associated with the 2 components, pharmacy enrolment, training and support and pharmacy consultation, will be prospectively identified, measured and valued. In measuring resource use associated with delivery of the intervention, data will be collected from the research team, from the enrolled pharmacies and from the enrolled patients. Labour time will be measured using opportunity costs and valued based on Pharmacy Industry Award rates of pay, and average earnings for patients.

Health care resource use will be captured per the secondary outcomes of the study. Primary care resource use will be measured from MBS records and valued based on current Medicare Benefits Schedule listed prices. Medication use will be valued using Pharmaceutical Benefits Schedule listed prices, over-the counter medication will be valued using market prices. Hospital utilisation will be measured using the APDC and EDDC and valued based on Independent Health and Aged Care Pricing Authority (IHACPA) National Efficient Price tariffs.

Results from the economic analysis will be expressed as (1) net benefit in terms of implementation costs and cost savings arising from more efficient treatment pathways; and (2) cost-consequence results accounting for patient experience measures, relevant safety outcomes and implementation measures.

Decision uncertainty will be accounted for using parametric and non-parametric bootstrapping to generate uncertainty intervals around the net benefit result.

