4.4.2 Participant inclusion criteria

Eligible participants must meet all the following criteria, which are included in the clinical management protocols (Appendix 1 & 2):

- Natal, cis females (capable of pregnancy).
- Aged 18 years of age or over and up to and including aged 35 years.
- Present to community pharmacies in NSW or pharmacies in ACT to obtain a continuing supply of their previously prescribed oral contraceptive pill.
- Patient has been initiated on an oral contraceptive pill by their GP (or other authorised prescribing health care professional) primarily for the indication of contraception and has been stabilised on that pill for 2 years continuously.
- Patient is taking an approved oral contraceptive pill listed in the NSW Health Authority.
- Patient has seen their GP (or other authorised prescribing health care professional) for a review of their oral contraceptive pill in the last 2 years.

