4.7.5 NSW Health Data

The George Institute will provide NSW Health with a list of study participants recruited at each site. This will include a study identification number generated at registration into the trial and the following identifiers: name, date of birth, address. NSW Health will then extract information for these participants on the variables listed in Appendix 28. The data period will include 12 months prior to the study registration date up to the most recent data available in the NSW Health data collections. A deidentified file including only the participant study ID number will then be sent to the George Institute for Global Health using a secure file transfer protocol.

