4.9 Outcomes

Primary outcomes

Primary outcomes will be accessibility and acceptability of the service (based on self-report at 7-day follow up). This will be a composite measure based on patient self-reported data. It includes seven items adapted from existing questionnaires, including a validated questionnaire for perceived service quality in community pharmacies (two items) and studies of pharmacy prescribing for oral contraception, and other medications [1-6]. It will cover the following domains: (a) trust and confidence in health and medical advice provided, (b) convenience, (b) privacy during discussion with pharmacy, and (b) overall satisfaction. Each item is scored on a 7-point Likert scale. Each domain will be equally weighted, and an aggregated score calculated and scaled to a maximum score of 100.

Secondary outcomes

- **On time dispensing rates**: 36 months pre and 12 months post introduction of the intervention (assessed using the proportion of days covered method using PBS data) [40].
- **Primary care utilisation:** MBS records will be used to measure use of general practice services prior up to 36-months pre and 12 months post introduction of the intervention date (MBS data).
- **Safety outcomes**: Adherence rates to Clinical management protocols (assessed by practice change facilitators conducting regular pharmacy monitoring and inspection of data from the patient consultation IT system), hospitalisation for potential pill-related adverse events (e.g., thromboembolic disease) (NSW Health data), rates of STI tests undertaken (MBS pathology data) and adverse events.
- **Implementation outcomes**: Implementation outcomes will also be assessed to examine the fidelity, reach and adoption of the new service, and barriers and facilitators to implementation.

• **Economic outcomes:** Results from the economic analysis will be expressed as (1) net benefit in terms of implementation costs and cost savings arising from more efficient treatment pathways; and (2) cost-consequence results accounting for patient experience measures, relevant safety outcomes and implementation measures. This will be assessed using multiple data sources including MBS records for 36 months pre and 12 months post introduction of the intervention.

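### Section 4.10.3 does not settle whether hospital and emergency costs are pill-related or all-cause; if all-cause, eligibility puts maternity care mainly on the follow-up side

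*Protocol*

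**What the plan says.** **Scope of costing.** Section 4.10.3 (Economic analysis) sets a general rule: "Health care resource use will be captured per the secondary outcomes of the study". Among the secondary outcomes in section 4.9, the only hospital item is "hospitalisation for potential pill-related adverse events (e.g., thromboembolic disease) (NSW Health data"), listed under safety. No emergency department outcome appears there. Later in the same paragraph of 4.10.3 comes the costing sentence: "Hospital utilisation will be measured using the APDC and EDDC and valued based on" the national efficient price. It names the admitted-patient and emergency collections and gives no limit by cause.

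**General practice use.** Section 4.9 states that "MBS records will be used to measure use of general practice services", without restriction by reason for the visit.

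**Windows.** The economic outcome draws on several sources, "including MBS records for 36 months pre and 12 months post introduction of the intervention" (4.9). For hospital data, section 4.7.5 says: "The data period will include 12 months prior to the study registration date up to the most recent data available". The look-back is fixed and the follow-up is not.

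**Eligibility.** Section 4.4.2 admits women capable of pregnancy who started an oral contraceptive mainly for contraception, and each participant "has been stabilised on that pill for 2 years continuously". It also requires a review of the pill by a GP or other prescriber within the last two years.

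**Net benefit.** Sections 4.9 and 4.10.3 describe it as implementation costs together with savings from more efficient treatment pathways. No formula is given. Section 4.2 describes a cohort design, and no control group is described.

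**The concern.** Two features combine. First, the protocol does not make clear which hospital and emergency contacts count. Second, the eligibility rule makes the period before registration unlike the period after it in one expensive respect. A woman who has taken the same pill without a break for two years has almost certainly not been pregnant in that time. After registration nothing selects women in this way. Some will stop the pill, and section 4.6.5 itself plans to look at discontinuation before and after the service.

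If all-cause use is compared before and after, antenatal care, pregnancy loss and birth admissions enter mainly the follow-up side. Costs would then rise without any effect of the service. The adjustment in section 4.10.1 (age, comorbidity count, earlier primary care use, SEIFA) works between women and cannot remove a shift within each woman that selection creates. Bootstrapping would widen the interval but leave the shift in place. A birth admission is costly next to a $20 consultation, so the sign of net benefit could depend on which of the two sentences in 4.10.3 is applied.

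**Working it through.** The protocol states no cost, pregnancy rate or sample size, so there is no planned figure to reproduce. The check compares the passages and then sets a scale.

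**1. Scope, side by side.**
- General rule (4.10.3 with 4.9): hospital use means possible pill-related admissions. A birth admission is out, and so is emergency use.
- Costing sentence (4.10.3): hospital utilisation from the admitted-patient and emergency collections, no cause named. Emergency use is in, and a birth admission may be.
- These cannot both define the base case.

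**2. Share of each look-back inside the continuous-pill period.** Formula: min(24, look-back months) / look-back months, assuming each window is counted back from the woman's registration.
- Hospital and emergency: 12/12 = 100%.
- MBS: 24/36 = 67%. Months 25 to 36 before registration may contain pregnancy care.

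**3. What can enter follow-up.** With 12 months of follow-up and about 9 months' gestation (assumed), a term birth falls inside only if conception occurs by month 12 − 9 = 3. Earlier pregnancy care, loss or termination can fall anywhere in the window. The open-ended hospital window in 4.7.5 admits later births unless it is cut.

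**4. Scale for hospital cost.** Let p be the share of women with a birth admission in follow-up and C its cost; both are assumptions. The look-back rate is about 0, so the mean shift per woman is p × C. It equals the $20 NSW consultation fee (4.5.4) when p = 20/C:
- C = $5,000: 20/5,000 = 0.4%.
- C = $10,000: 20/10,000 = 0.2%.
- C = $15,000: 20/15,000 = 0.13%.

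For illustration, suppose 2% to 8% of women conceive by choice in 12 months, evenly spread. Births inside the window are then 2% × 3/12 = 0.5% to 8% × 3/12 = 2%. The shift runs from 0.005 × $5,000 = $25 to 0.02 × $15,000 = $300 per woman.

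**5. Direction for general practice use.** Two features work against a simple conclusion.
- Dilution: if months 25 to 36 carry pregnancy visits at the same yearly rate as follow-up, the annualised shift falls to 1 − 12/36 = 2/3 of its size. With an assumed 2 to 6 antenatal visits per pregnancy, the undiluted shift is 0.02 × 2 = 0.04 to 0.08 × 6 = 0.48 visits per woman. Diluted, it is about 0.03 to 0.32 per year. The upper end is a ceiling, because it places every antenatal visit inside follow-up.
- Required review: entry demands at least one prescriber review in the look-back and follow-up has no such requirement. One visit over 36 months is 1/3 = 0.33 per year. The excess due to selection is smaller where the woman would have been reviewed anyway or where the reviewer was not a GP.

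These effects have opposite signs and may be of similar size, so the net direction is not determined.

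**The case against.** The strongest reply is that the opening rule of the resource-use paragraph in 4.10.3 governs what follows. The two collections are then only data sources, and hospital costing is already confined to pill-related events. Net benefit is described through savings from treatment pathways, which points to attributable costs and not to an all-cause difference. The hospital look-back in 4.7.5 is an extraction window, and pre and post windows are set out only for MBS data and dispensing. Code lists and attribution rules commonly sit in an analysis plan, which is not shown.

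Much of this stands. A reader might infer that the protocol costs all hospital use without restriction and therefore charges maternity care to the service. The text does not support that: the scope is contradictory, and no before/after formula for hospital cost is stated. Nor does it support a firm claim that the general practice comparison is biased against the service.

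Two parts of the reply do not stand. The conflict lies between two sentences of the protocol, so it is more than detail left for later; emergency records would serve no purpose under the narrow rule as 4.9 now lists the outcomes. And the only comparison described is a single cohort before and after, so the selection matters wherever unrestricted use is compared, as it is for general practice.

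It is also fair that the magnitudes are assumed and the upper ends doubtful. Women who have just asked for re-supply of up to 12 months are unlikely to conceive evenly from the first month. Removing pregnancy costs outright would be wrong too, because section 3.1 gives fewer unintended pregnancies as part of the rationale.

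**Conclusion.** The concern holds in conditional form. Section 4.10.3 is inconsistent on whether hospital and emergency costs are pill-related or all-cause, and general practice use is unrestricted. Eligibility makes all 12 hospital look-back months and 24 of 36 MBS months nearly free of pregnancy care, and follow-up is not so selected. If all-cause hospital use is compared before and after, the bias runs against the service. For general practice use the sign is open.

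The size is unknown. At an assumed $5,000 to $15,000 per birth admission, births in 0.4% to 0.13% of women offset the consultation fee, so even a low rate could matter to net benefit. This rests on the assumed unit costs, on windows counted from registration, and on the two-year criterion being applied as written in 4.4.2; it is not repeated in the synopsis, the aim or the exclusion list. The point should be settled before results are seen. It affects a secondary economic outcome and general practice use, not the primary outcome.

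**What to change.** In sections 4.9 and 4.10.3:

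- Reconcile the two sentences: state whether hospital and emergency costing is pill-related or all-cause, and if emergency use counts, name it as an outcome.
- Set equal, fixed windows before and after registration for hospital and emergency data, in place of the open-ended follow-up in 4.7.5.
- Report pregnancy-related MBS and hospital use as its own line, and show net benefit both with and without it. This keeps contraceptive failure and avoided pregnancy visible.
- Add a sensitivity analysis of general practice use that censors each woman at her first pregnancy-related record.

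The cost is some wording and a code list applied to data already requested. The downside is small: readers have two net-benefit figures to interpret, and the text must say which is the base case.

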4.10.4 Implementation outcomes analysis

The implementation component of the study will be underpinned by the Consolidated Framework for Implementation Research (CFIR) [41-44], in particular the use of an adapted implementation model for community pharmacy [45-55]. Implementation factors (barriers, causes and facilitators) (Appendix 3) and the Dougherty strategy classification systems (Appendix 4), adapted to community pharmacy, will be used [45-55]. This will build on the trial outcomes to determine scalability of the intervention. The evaluation framework is set out in Figure 1. The CFIR domains and sub-domains will also be used to organise the data. Descriptive statistics be produced for all implementation outcomes. Links between implementation barriers and facilitators, their cause and implementation strategies will be visually represented using Sankey diagrams. A predictive resolution percentage will be calculated using random forest method for predicting effective strategies for all implementation barriers.

[figure not shown]

Figure 1 Implementation Evaluation Framework adapted from Moullin, et al. [45]

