4.2 Study design

The study hypothesis will be tested using a cohort study design, applying mixed methods (quantitative and qualitative research) to assess clinical and economic indicators, implementation, and patient experience.

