4.5.3 Implementation strategy

There will be follow up training and ongoing support as part of a translational/implementation strategy through the study period. Practice change facilitators will visit participating pharmacies to provide ongoing support, answer any queries, ensure quality data is being collected, and collect implementation data. The implementation component of the study will be underpinned by the Consolidated Framework for Implementation Research (CFIR), with the use of an adapted implementation model for community pharmacy. Implementation factors (barriers, causes and facilitators) and the Dougherty strategy classification systems, adapted to community pharmacy, will be used.

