4.6.3 Implementation data

Practice change facilitators: The collection of the implementation data will be undertaken through visits/contacts (approximately monthly) within the resources available depending on the final number of community pharmacies participating, by practice change facilitators employed as part of the project. An openended discussion which, depending on the mode of contact, will vary between 10 to 20 minutes (see Appendix 23 for an implementation checklist to be used by practice change facilitators). Data will be collected using a pre-developed form in REDCap. Practice change facilitators will be trained by an implementation expert on models and frameworks of implementation science with an emphasis on the application of these to this specific study and the use of the checklist for data collection purposes.

Semi-structured interviews: The perspectives and experiences of community pharmacists and participants (patients) will be captured at 6 months and 10 months using semi-structured interviews undertaken by the George institute . Perspectives of other stakeholders will also be sought including general practitioners, professional bodies including the Pharmacy Guild, Pharmaceutical Society of Australia and the Royal Australian College of General Practitioners, and NSW Health administrators.

A maximum variation sampling technique will be used to select a diverse range of pharmacies and patients for interviews, taking into consideration pharmacy level factors such as geography, pharmacy size and participant level factors such as age, geography, presence of comorbid conditions, income status. It is anticipated that around 50 interviews in total will be conducted, however, the final sample size will be determined when it is considered the research team have achieved thematic saturation and few new themes are emerging from the interviews.

For participants (patients), interview questions will focus on experiences of health care and awareness and perceptions of services (Appendix 21). They will take no longer than 45 minutes. For community pharmacists and other stakeholders', questions will focus on implementation and contextual factors which may influence

program outcomes [36-39], sustainability, staff experiences and motivation to engage in the prescribing model (Appendix 26). These interviews will take up to 1 hour.

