4.7.4 Implementation data

Practice change checklists: Data from the checklists developed by Practice Change Facilitators will be entered into Redcap. A deidentified file including only pharmacy identification number will be securely sent by the UoN research team to the George Institute for analysis.

Interviews: Lists of patient participants that expressed they are willing to be contacted for an interview on the consent form will be generated. A diversity sample will be constructed from these lists to include a range of socio-economic status, living situation (independent/ other), morbidities and engagement with the initiative. Lists of health system administrators and providers will include those directly or indirectly involved in the initiative. The study team will contact eligible participants to invite them to participate and request a time for an interview/focus group. Non-responding eligible participants will be followed up a maximum of two times. At the scheduled interview all participants will be given a full explanation of the study by the research team and provided with an opportunity to ask questions. Consenting participants will be allocated the unique study ID number generated at the baseline registration visit. Interview data will include files of audio and video recordings and transcripts of interviews/focus groups. Audio or videoconference files of interviews will be transcribed verbatim by a professional transcription service after a confidentiality agreement has been signed.

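### Section 4.10.4 treats a random-forest prediction from observed, non-assigned strategy use as showing which implementation strategies are effective; if strategy choice depends on barrier difficulty, the prediction may understate or even reverse a strategy's advantage

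*Protocol*

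**What the plan says.** Protocol 4.10.4 sets out the implementation analysis: descriptive statistics, Sankey diagrams linking barriers, causes and strategies, and then a model. "A predictive resolution percentage will be calculated using random forest method for predicting effective strategies for all implementation barriers". The classification inputs are given in the same section: "Implementation factors (barriers, causes and facilitators) (Appendix 3) and the Dougherty strategy classification systems (Appendix 4), adapted to community pharmacy, will be used". An earlier sentence there says that the implementation component as a whole will help to determine scalability.

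On design, 4.2 says: "The study hypothesis will be tested using a cohort study design, applying mixed methods". No random or rule-based assignment of strategies to barriers appears anywhere.

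On the data, 4.5.3 says: "Practice change facilitators will visit participating pharmacies to provide ongoing support, answer any queries, ensure quality data is being collected, and collect implementation data". Section 4.6.3 adds: "The collection of the implementation data will be undertaken through visits/contacts (approximately monthly) within the resources available". Each contact is an open-ended discussion whose length, "depending on the mode of contact, will vary between 10 to 20 minutes". Section 4.7.4 names the source of the analysis file: "Data from the checklists developed by Practice Change Facilitators will be entered into Redcap".

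The protocol does not say who selects a strategy, how it is selected, or who decides that a barrier is resolved. Barrier severity, time open and number of earlier attempts are not named as variables. The covariates in 4.10.1 (age, comorbidity count, prior primary care use, SEIFA) describe patients and their areas, not barriers.

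**The concern.** A random forest fitted to records of what was done predicts how often barriers were resolved when a given strategy was used. Whether the strategy is effective is a different question: what would have happened to the same barrier under another strategy. The two answers agree only if, given the model inputs, strategies were used on comparable barriers. Nothing in the design secures that. If more intensive strategies tend to go to harder barriers, or are tried after another has failed, the prediction mixes the strategy's effect with the barrier's difficulty.

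Two features add to this. Asking for a figure for every barrier means that pairs of barrier and strategy rarely or never seen together still receive a number, borrowed from other records. And the people who support the pharmacies also collect the data, with no independent rating of resolution described; this could bias results in either direction.

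At stake is the advice on which strategies to use for which barriers, which forms part of a component meant to inform scalability.

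**Working it through.** The protocol gives no resolution rate, sample size or other figure for this analysis, so there is nothing to reproduce. All rates below are assumptions, used to find the direction of the bias and the conditions under which it matters.

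**Step 1. Two strata, by hand.** Barriers are easy or hard. Strategy A resolves a proportion e of easy and h of hard barriers; B is truly better by d in both. The shares of hard barriers are sA and sB. Then:

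crude A = e(1 - sA) + h·sA

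crude B = (e + d)(1 - sB) + (h + d)·sB

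crude B - crude A = d - (sB - sA)(e - h)

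The order reverses only if (sB - sA)(e - h) exceeds d.

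| e / h | d | hard share A / B | crude A | crude B | B - A |
|---|---|---|---|---|---|
| 80% / 40% | 5 | 50% / 50% | 60.0% | 65.0% | +5.0 |
| 80% / 40% | 5 | 40% / 60% | 64.0% | 61.0% | -3.0 |
| 80% / 40% | 5 | 30% / 70% | 68.0% | 57.0% | -11.0 |
| 70% / 50% | 10 | 30% / 70% | 64.0% | 66.0% | +2.0 |
| 70% / 50% | 10 | 20% / 80% | 66.0% | 64.0% | -2.0 |
| 65% / 55% | 10 | 20% / 80% | 63.0% | 67.0% | +4.0 |

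The full grid has 24 scenarios: three pairs e / h (80/40, 70/50, 65/55), d of 5 or 10 points, and four splits (50/50, 40/60, 30/70, 20/80). The 6 with equal shares return d exactly. Of the 18 with unequal shares, all understate d and 9 reverse the order. That is a count over a chosen grid, not a probability. Comparing within a stratum returns d every time.

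**Step 2. Allowing for barrier type.** Section 4.10.4 ties the prediction to barriers and records causes, so the fair test compares strategies within barrier type. Assumed model: difficulty D is standard normal; logit of resolution = 0.3 + 0.5 × intensive - 1.0 × D (odds ratio exp(0.5) = 1.65, about +10 points on average); logit of choosing the intensive strategy first = -1 + D; after a failure, the second attempt is intensive with probability 0.8. There are 20 barrier types, which explain a set share of the variance of D. Resolution rates within type stand in for a forest that has type and strategy as inputs and ample data.

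| Share of difficulty explained by type | Estimated difference (points), true about +10 |
|---|---|
| 0% | -3.8 |
| 25% | -0.9 |
| 50% | +2.5 |
| 75% | +5.9 |
| 90% | +8.6 |

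**Step 3. Weaker selection.** With both slopes on D halved to 0.5 and 65% of second attempts intensive, the within-type estimate runs from +7.1 to +10.5 against a true +11.1. The order is kept and the difference shrinks.

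**Step 4. What attempt order adds.** If first choice is unrelated to difficulty and only second attempts favour the intensive strategy, ignoring attempt order gives +5.7 to +9.6, and comparing within type and attempt restores about +10. If first choice also depends on difficulty, attempt order removes only part of the bias.

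**The case against.** The strongest reply has four parts.

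First, the mechanism is assumed. A reader might infer from 4.5.3, 4.6.3 and 4.7.4 that facilitators choose the strategies, score the results themselves, escalate when a barrier persists and keep some strategies for hard cases. The protocol says none of this, only that facilitators give support, make contact about monthly as resources allow, and supply the checklists. This stands, and it is why the point is conditional.

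Second, a forest on strategy alone can be made to put a better strategy about 5 points worse, and a reader might take that as the expected result. It is not the analysis in 4.10.4, which predicts by barrier and has causes on record. This also stands: step 2 shows that conditioning on type removes much of the bias where type is informative about difficulty.

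Third, model inputs, validation and minimum cell counts usually belong in a statistical analysis plan, which is not shown. Nor are the checklist (Appendix 20) and Appendices 3 and 4, which may already record dates and attempts. This stands for the details, so their absence is not held against the protocol. It does not answer the main point: the step from a predicted percentage to effective strategies, for all barriers, is written in the protocol itself.

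Fourth, the consequence is limited. One might read 4.10.4 as letting a ranking of strategies drive roll-out. The scalability sentence comes before the model and concerns the whole implementation component, and no ranking rule is stated. That stands too.

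**Conclusion.** The point holds in conditional form. Section 4.10.4 labels as effective what is only predicted under observed use, and the design gives no ground for the stronger word. If choice of strategy depends on difficulty or earlier failure, the percentage may understate the advantage of strategies used on harder barriers, even within barrier type. Under the assumed strong selection, a true difference of about +10 points appears as anything from +8.6 to -3.8; under weaker selection, a true +11.1 appears as +7.1 to +10.5.

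It does not follow that better strategies will be ranked as worse. Reversal needs strong selection together with barrier types that say little about difficulty: in step 2 it occurs at 0% and 25% explained but not from 50% upwards. All these sizes rest on assumed rates and selection. The matter is confined to a secondary implementation analysis and does not touch the primary outcome in 4.9.

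**What to change.** In 4.10.4:

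- Describe the output as predicted resolution under observed use, and state that it is not evidence of a strategy's effectiveness.
- Compare strategies by setting each in turn for the same barrier records and averaging the predictions. Use only information known before the strategy was chosen: barrier, cause, pharmacy and facilitator, plus time open and number of earlier strategies where the checklist records them.
- Check prediction on whole pharmacies held out of the fitting, since records cluster by pharmacy.
- Give no figure for a barrier-strategy pair not used in a stated minimum number of pharmacies.
- State who judges a barrier resolved.

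The cost is mostly wording. If the REDCap checklist does not already carry the contact date and attempt number, those two fields need adding before or early in data collection, because a later analysis plan cannot recover them. Some barrier-strategy pairs will carry no figure, so the promise of a result for all barriers has to be dropped. Confounding by difficulty that nobody recorded will remain, which is why the relabelling is needed even if everything else is done.
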